9.4 Safety Analysis

The overall safety profile of VX-150 will be assessed in terms of the following safety and tolerability endpoints:

- Incidence of treatment-emergent adverse events (TEAEs)
- Clinical laboratory values (hematology, serum chemistry, coagulation studies, and urinalysis)
- ECG outcomes
- Vital signs

Safety analyses will be based on the Safety Set.

Safety analyses will be based on the Safety Set and subjects will be analyzed according to the treatment they actually received. In an unexpected scenario that a subject may receive more than one treatment in the study, the following algorithm will be used to define subject's actual treatment: for any dosed subjects, if the subject receives more than one dose level of VX-150, the actual treatment is defined as the highest dose level among all received VX-150 treatment, regardless of the randomized treatment assignment. For any dosed subjects, the actual treatment is defined as placebo only if the subject receives placebo at all visits in the study.

9.4.1 Adverse Events

AEs will be coded according to MedDRA. The number and percentage of subjects experiencing an AE will be summarized by the MedDRA System Organ Class and preferred term, as well as by treatment group. AEs will be classified as pretreatment or treatment-emergent as follows:

Pretreatment AEs are defined as AEs that were reported or worsened after signing the ICF up to the start of study drug dosing.

Treatment-emergent AEs are defined as AEs that were reported or worsened on or after the first dose of study drug through the end of the TE period.

Details for imputing missing or partial start date and time of adverse events are described in Appendix C.

Only TEAEs will be summarized in tables. All summaries of TEAEs will be presented by the severity of the AE and relationship to the study drug. Some rules that will apply to the summarization of AEs are (1) a subject with multiple occurrences of the same AE or a continuing AE will only be counted once; (2) only the maximum severity level will be presented in the severity summary; and (3) only the strongest relationship level will be presented in the relationship summary. An AE with relationship missing is counted as related AE.

SAEs, AEs leading to death, and AEs leading to study drug interruption and study drug treatment discontinuation will be listed separately. All AEs through Safety Follow-up will be listed in an individual subject data listing, including pretreatment AEs.

9.4.2 Clinical Laboratory Assessments

All statistical analyses of laboratory values will be performed using International System of Units. Hematology and clinical chemistry results at baseline will be summarized by treatment group. Other assessments will be collected as needed, i.e. at unscheduled visits. The threshold value criteria for hematology and clinical chemistry laboratory tests are provided in Appendix D. A listing containing individual subject hematology and clinical chemistry measurements meeting the threshold value criteria at any visit will be provided. For each subject in the listing, measurements at all visits will be included. Results of coagulation, urinalysis and the urine/serum pregnancy test will be presented in individual subject data listings only.

Clinically significant abnormal laboratory findings will be reported as AEs.

9.4.3 Electrocardiogram

A summary of raw values and change from baseline values will be provided by treatment at each scheduled time point during the TE period for the following standard 12-lead ECG measurements: PR, QT, QRS, QTcF [QTcF = QT/RR^{0.33}], and HR. In addition, the number and percentage of subjects by maximum on-treatment value of QT/QTcF intervals, categorized as \leq 450 msec, >450 msec and \leq 480 msec, >480 msec and \leq 500 msec, and >500 msec, as well as maximum on-treatment change from baseline value of QT/QTcF intervals, categorized \leq 30 msec, >30 and \leq 60 msec, and >60 msec, will be provided.

The threshold value criteria for ECG data are provided in Appendix D. A listing containing individual subject measurements meeting the threshold value criteria at any time point will be provided. For each subject in the listing, ECG measurements at all time points will be included.

Clinically significant ECG abnormalities occurring during the study through the Safety Follow-up will be recorded as AEs.

9.4.4 Vital Signs

The raw values and change from baseline values during the TE period will be summarized by treatment at each scheduled visit: systolic and diastolic blood pressure (mm Hg), body temperature (°C), pulse rate (beats per minute), and respiratory rate (breaths per minute).

The threshold value criteria for vital signs data are provided in Appendix D. A listing containing individual subject measurements meeting the threshold value criteria at any visit will be provided. For each subject in the listing, vital signs at all visits will be included.

Clinically significant abnormal findings in vital signs will be reported as AEs.

9.4.5 Physical Examination

PE results will be presented in individual subject data listings only. Clinically relevant results identified after screening will be reported as AEs.

10 SUMMARY OF INTERIM AND IDMC ANALYSES

Not applicable.

12 LIST OF APPENDICES

Appendix A: Analysis Visit Windows for Safety and Efficacy Assessments

Assessment	Visit/Time Point ¹	Target Study Day /Time Point per the protocol	Analysis Visit Window (in study days/ time points)
Safety Assessment			
Hematology Serum Chemistry Coagulation	Baseline	-1	[Screening visit, Pre-dose Day 1]
Standard 12-Lead ECG	Baseline	1	[Screening visit, Pre-dose Day 1]
	Day 1, 4 hours	4 hours after the first dose of study drug	3 – 5 hours after the first dose of study drug on Day 1
Vital Sign	Baseline	1	[Screening visit, Day 1]
	Day 2	2	2
	Day 3	3	3
Efficacy Assessment			
NPRS	Baseline	1	[After removal of the popliteal sciatic block, Pre-dose Day 1]
	At 0.5, 1, 1.5, 2, 3, 4, 5, 6, 8, 12, 16, 20, 24, 28, 32, 36, 40, 44, and 48 hours	1 - 3	± 5 minutes for 0.5 to 12 hours ± 10 minutes for 16 to 48 hour
VRS	Baseline	1	[After removal of the popliteal sciatic block, Pre-dose Day 1]

Notes:

The analysis visit windows will be applied using the following rules for both scheduled and unscheduled visits:

- 1. If no numerical measurement is available within a visit window, the measurement will be considered missing for the visit.
- 2. If there is more than 1 numerical measurement available within the same visit window, use the following rules:
 - a. a. For efficacy assessments: if there are multiple measurements within a visit window,
 - i. The measurement closest to the target day/time point will be used; or
 - ii. If there are multiple measurements within the same distance from the target day/time point, the latest measurement will be used.
 - b. For **safety** assessments: if there are multiple measurements within a visit window,
 - i. The measurement closest to the target day/time point will be used; or

¹Visit/Time point name for analysis purpose is used to report data in tables and figures.

Protocol Number: VX18-150-104

- ii. If there are multiple measurements within the same distance from the target day/time point, the latest measurement will be used.
- 3. When define efficacy and safety at baseline, refer to the generic baseline definition in Section 9.1. If hour and/or minute of first dose time are missing, baseline will be defined as the most recent non-missing measurement collected before the date of first dose of study drug.
- 4. For vital sign, if scheduled and unscheduled measurements at the same date, the scheduled measurement will be used.
- 5. Age (in years) at first dose date (for demographics, listing):

Obtain the age at screening visit (in days) in "yy, mm" format (e.g., 24 years, 6 months) from the Vital Signs (VS) page at the Screening Visit, and add 0.5 month to convert to days.

Obtain the screening visit date.

Then age (in years) at first dose = [(first dose date– screening visit date) in days + age at screening visit (in days)]/365.25.

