Medications review	Continuous from signing of ICF through Safety Follow-up Continuous from signing of ICF through Safety Follow-up				
Treatments and procedures review					

β-hCG: beta-human chorionic gonadotropin; CRU: clinical research unit; NPRS: Numeric Pain Rating Scale; PK: pharmacokinetic; VRS: Verbal Categorical Rating Scale

Starting on Day 1, subjects will report their pain on the NPRS at 0.5, 1, 1.5, 2, 3, 4, 5, 6, 8, 12, 16, 20, 24, 28, 32, 36, 40, 44, and 48 hours (± 5 minutes) after the first dose of study drug. In addition, pain intensity on the NPRS will be recorded when the subject requests the first dose of study drug for pain relief and immediately before each administration of rescue medication.

Continuous from signing of ICF through Safety Follow-up

on Day 1, subjects will report their pain on the VRS when they request the first dose of study drug for pain relief.

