9.3.2 Study Drug Dose and Duration

Five dose levels of VX-150 (Dose Levels 1 [highest], 2, 3, 4, and 5 [lowest]) will be evaluated as shown in Table 9-1. The highest dose level (Dose Level 1 [first dose 1500 mg, then 750 mg every 12 hours (q12h)]) will not exceed a maximum dose of 2250 mg per day. The maximum dose has been selected on the basis of favorable safety and VRT-1207355 PK results after oral dosing with VX-150 in

VX16-150-103 (Study $\overline{103}$). Multiple oral doses up to 1750 mg qd VX-150 for 14 days have been evaluated and found to be safe and well tolerated. Additionally, the treatment duration is the same as in Study 103.

The highest dose level (Dose Level 1) to be tested (2250 mg per day; first dose 1500 mg followed by doses of 750 mg q12h) was evaluated in Study 103 in subjects with acute pain following bunionectomy. After administration of the first dose of VX-150 on Day 1 and Day 2, the mean VRT-1207355 maximum observed concentration (C_{max}) of 4.95 µg/mL (Day 1) and 4.92 µg/mL (Day 2) exceeded the concentration resulting in 50% of the maximum inhibition (IC_{50}) for inhibition of Na_v1.8. The maximum concentrations for VRT-1207355 were reached approximately 5.58 hours after the first dose on Day 1 and 4.03 hours after the first dose on Day 2. A statistically significant treatment effect was observed at 24 hours following the first and second doses, favoring VX-150 compared to placebo. VX-150 was generally well tolerated in these subjects without any significant safety concerns.

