9 STATISTICAL ANALYSIS

9.1 General Considerations

The Schedule of Assessments is provided in Section 3 of CSP. The precision standards for reporting safety and efficacy variables are provided in an internal Biometrics document that specifies the programming rules including the precision for derived variables.

Continuous variables will be summarized using the following descriptive summary statistics: the number of subjects (n), mean, standard deviation (SD), median, minimum value (min), and maximum value (max), unless otherwise specified.

Categorical variables will be summarized using counts and percentages.

Baseline value for NPRS will be defined as the most recent non-missing measurement collected on Day 1 before the first dose of study drug. For all other variables, unless

Protocol Number: VX18-150-104

otherwise specified, baseline value will be defined as the most recent non-missing measurement (scheduled or unscheduled) collected before the first dose of study drug.

Change (absolute change) from baseline will be calculated as post-baseline value – baseline value unless otherwise specified.

Treatment-emergent (TE) Period will be defined as the time from first dose of study drug through the Safety Follow-up (for enrolled subjects who do not have a Safety Follow-up Phone Interview: it will be defined as the time from first dose of study drug through 9 days after the last dose of study drug)

Unscheduled visits: Unscheduled visit measurements will be included in analysis as follows:

- In scheduled visit windows per specified visit windowing rules.
- In the derivation of baseline/last on-treatment measurements.
- In the derivation of maximum and minimum values during TE period, and maximum and minimum change from baseline values during TE period for safety analyses
- In individual subject data listings as appropriate.

Visit windowing rules: The analysis visit windows for protocol-defined visits are provided in Appendix A.

Incomplete/missing data will be imputed for NPRS by applying linear interpolation to the valid observations immediately before and after the missing observation(s). If there are no valid observations after the missing observation(s) the last observation carried forward (LOCF) principle will be applied as a primary approach. Additional details on how to handle missing data is described in subsequent sections when applicable.

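### A scheduled NPRS score taken minutes outside the SAP analysis window is discarded and replaced from scores hours away; the group effect is probably small and the correction is cheap

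*SAP*

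**What the plan says.** **Collection.** The NPRS footnote to Protocol Table 3-2 sets one tolerance for every time point: "28, 32, 36, 40, 44, and 48 hours (± 5 minutes) after the first dose of study drug". The protocol does not say that a score outside it is invalid.

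**Analysis windows.** The NPRS row of SAP Appendix A gives ± "5 minutes for 0.5 to 12 hours ± 10 minutes for 16 to 48 hour". Note 1 below the table adds: "If no numerical measurement is available within a visit window, the measurement will be considered missing for the visit". The windows apply to scheduled and unscheduled scores alike, and the score closest to target is used.

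**Filling the gap for SPID24.** SAP 9.1 and 9.3.1.1 interpolate an intermittent missing score linearly between the nearest valid scores on either side, over 0 to 48 hours. They assume such gaps are missing completely at random. Section 9.3.1.1 makes this step 1 of the imputation order, rescue replacement step 2, and filling of data missing up to the endpoint step 3. The same section also prescribes LOCF when scores are missing from some time point up to hour 24, even in a subject who completes the study.

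**Filling the gap for responders.** SAP 9.3.2.1 has its own rule. A subject still on study drug with no 24-h score takes the last eligible earlier score.

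**Dosing times.** Under Protocol 9.1 and 9.6, capsules are given every 12 hours, the last at 36 hours. By Table 9-1, Dose Levels 1, 3 and 4 are dosed every 12 hours after the first dose, while Dose Levels 2 and 5 are once daily.

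**The concern.** A tolerance meant for site conduct has become a rule for discarding data. A 12-h score taken 6 minutes late, or a 24-h score taken 11 minutes late, was observed; it is not missing. No window-assignment problem calls for this, because the closest scheduled times are 30 minutes apart and from 8 h onward they are 4 hours apart.

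The replacement is the weaker measurement. The 12-h and 24-h scores fall at the end of a dosing interval, whereas the 16-h and 28-h scores fall 4 hours after the next dosing time. For the Dose Level 1 regimen in the earlier bunionectomy study, Protocol 9.3.2 puts peak concentration at about "4.03 hours after the first dose on Day 2", so a 28-h score could sit near peak exposure. At 12 h the next dose is active only in Dose Levels 1, 3 and 4, so a substitution error there can differ by arm. SAP 9.3.1.2 pools Levels 2 and 3, which mixes the two situations within one analysis group. In a trial whose primary objective is dose-response, an error that depends on the regimen is unwelcome even if it is small.

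**Working it through.** **1. The plan's own yardstick.** No design figure is in dispute, but the planned effect size scales the result. SAP 7.2 gives 40 evaluable subjects per arm, an effect of 0.7 SD, a 5% level and at least 85% pairwise power. Noncentrality is 0.7 × √(40/2) = 3.13, and 3.13 − 1.96 = 1.17, which gives power of 0.879 (normal) or 0.871 (t, 78 df). Both meet the stated floor.

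**2. Weights.** SAP 9.3.1.1 weights each score by hours since the previous one: 12 − 8 = 4 and 24 − 20 = 4. Each is 4/24 = 16.7% of the interval, and together they are 8/24. A 1-point error at either time moves that subject's SPID24 by 4.

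**3. What fills the gap** when the scheduled neighbours are the nearest valid scores:
- 12 h: (score at 8 h + score at 16 h)/2
- 24 h by interpolation: (score at 20 h + score at 28 h)/2
- 24 h by LOCF: score at 20 h

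Under interpolation, the score from after the next dosing time supplies 50% of the value.

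**4. One subject, SPID24 (assumed scores).** Baseline 8; 20 h = 6; 24 h 11 min = 7; 28 h = 4.
- Interpolation: (6 + 4)/2 = 5. Error 7 − 5 = 2 points; 2 × 4 = 8 SPID24 units too favourable.
- LOCF: 6. Error 7 − 6 = 1 point; 1 × 4 = 4 units too favourable.

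**5. One subject, responder status (assumed scores).** Only LOCF applies, and the error can go either way.
- Baseline 8; 20 h = 6; 24 h 11 min = 4. Observed reduction (8 − 4)/8 = 50%; LOCF gives (8 − 6)/8 = 25%. A subject meeting the 30% and 50% criteria meets none.
- Baseline 7; 20 h = 4; 24 h 11 min = 6. Observed reduction (7 − 6)/7 = 14%; LOCF gives (7 − 4)/7 = 43%. A non-responder becomes a 30% responder.

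**6. Group level.** The documents give neither the rate of out-of-window scores nor the SD of SPID24, so both are assumed. Let f be the share out of window at each of 12 h and 24 h, and e the mean between-arm difference in substitution error. The shift in a between-arm difference is f × (4 + 4) × e = 8fe. With SD 30 to 60, a 0.7-SD effect is 21 to 42 units.

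| f | e (points) | shift 8fe | share of 0.7-SD effect (SD 60 to SD 30) |
|---|---|---|---|
| 1% | 0.5 | 0.04 | 0.1% to 0.2% |
| 5% | 1 | 0.4 | 1.0% to 1.9% |
| 10% | 1 | 0.8 | 1.9% to 3.8% |
| 20% | 2 | 3.2 | 7.6% to 15.2% |

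At f = 5%, with lateness independent at the two times, 1 − 0.95² = 9.75% of subjects have at least one of these two scores replaced. If the error is the same in both arms, e = 0 and the contrast is unaffected.

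**The case against.** The strongest defence is that the windows are prespecified and nowhere narrower than the protocol's tolerance, and that from 16 h they are twice as wide. Subjects are inpatients throughout, so few scores should fall outside. This stands as an argument about size: nothing in the documents suggests that late scores are common. It does not justify the rule, because a score measured minutes off target is better information than one built from scores 4 hours away.

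The LOCF wording in SAP 9.3.1.1 could also govern a missing 24-h score. That would halve the error in the SPID24 example and keep the post-dose score out. This stands in part. The imputation order and the 0-to-48-hour range favour interpolation when a 28-h score exists, but the text does not settle it.

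It can be argued that the late score could itself serve as an interpolation neighbour, giving 6 + 4/4.183 = 6.96 in the example and almost no error. The SAP does not define a valid observation, but note 1 treats the late score as missing and no rule readmits it, so this reading lacks support. A pre-rescue score may, however, be the nearest valid neighbour in some subjects.

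The peak-concentration figure is for plasma, at one dose level, in another study. It makes a post-dose difference in pain plausible but does not measure one.

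A reader might infer that relief after the next dose also enters responder status. It does not: SAP 9.3.2.1 carries an earlier score forward and never uses the 28-h score. A reader might also infer that the primary result is materially biased. Without a rate of late scores, the documents do not support that.

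**Conclusion.** The rule discards observed scores and substitutes worse values at two points that carry 8 of the 24 hours in SPID24. That follows from the text: without qualification at 12 h when the neighbouring scores are the scheduled ones, and at 24 h under step 1 of the imputation order. Responder status can change in either direction through LOCF from an earlier score.

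For one subject the effect can be appreciable: 4 SPID24 units per point of error, or a changed responder classification. For the group it is probably small, about 1–2% of a 0.7-SD effect at an assumed 5% late rate, 1-point differential error and SD of 30–60. It reaches 8–15% only with 20% late scores and a 2-point differential error. This is a cheap improvement to make before database lock, together with one ambiguity to resolve (interpolation or LOCF at 24 h). It is not a threat to the trial's conclusions.

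**What to change.** In SAP Appendix A:

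1. Keep ±5 minutes as the conduct target, and assign each observed scheduled NPRS score to its nominal time through wider, half-open windows. For example, use [t − 15 min, t + 15 min) for 0.5–2 h and [t − 30 min, t + 30 min) for 3–48 h. Half-open limits matter because closed windows of these widths would share endpoints, for instance at 0.75 h and 3.5 h.
2. Within a window, prefer the scheduled score over any unscheduled or pre-rescue score. Do not let an unscheduled score outside the current ±5 or ±10 minutes stand in for a scheduled one.
3. Impute only when no scheduled score was taken, and continue to apply the rescue rule by actual clock time.

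In SAP 9.3.1.1, state whether interpolation or LOCF fills a missing 24-h score for SPID24 when later scores exist.

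The cost is one table row, a revised selection rule for NPRS and one clarifying sentence. The downside is that some scores will sit up to 30 minutes from nominal time, and a late 12-h or 24-h score may fall shortly after the next dose.

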8.1 Inclusion Criteria

Before surgery:

- 1. Subject will sign and date an informed consent form (ICF)
- 2. Willing and able to comply with scheduled visits, treatment plan, study restrictions, laboratory tests, contraceptive guidelines, and other study procedures
- 3. Body mass index (BMI) of 18.0 to 38.0 kg/m², inclusive

- 4. Subjects (male and female) will be between the ages of 18 and 65 years, inclusive
- 5. Be scheduled to undergo a primary unilateral first metatarsal bunionectomy repair, without collateral procedures, under regional anesthesia (Mayo and popliteal sciatic block) not to include base wedge procedure

After surgery:

- 6. Subject reported pain of ≥4 on the NPRS and moderate or severe pain on the Verbal Categorical Rating Scale (VRS) within 9 hours after removal of the popliteal sciatic block on Day 1.
- 7. Subject is lucid and able to follow commands.
- 8. All analgesic guidelines (Section 9.4.1) were followed during and after the bunion ectomy.

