9 STUDY IMPLEMENTATION

9.1 Study Design

This is a Phase 2B randomized, double-blind, placebo-controlled, dose ranging, 6-arm, parallel-design study. Subjects will receive a primary unilateral first metatarsal bunionectomy repair on Day -1 (Figure 9-1). A continuous popliteal sciatic block infusion (0.2% ropivacaine) will be started after surgery and will be removed between 3AM and 5AM on Day 1. After removal of the popliteal sciatic block, a subject can be randomized once the subject requests the first dose of study drug for pain relief, and the subject's pain is ≥4 on the NPRS and is moderate or severe on the VRS. If a subject does not meet the NPRS and VRS criteria within 9 hours of removal of the popliteal sciatic block, the subject will not be eligible to enroll in the study.

A total of approximately 242 subjects will be randomized 2:2:2:2:1:2 to 6 treatment arms, evaluating a range of 5 VX-150 dose levels as shown in Table 9-1.

Table 9-1 VX-150 Doses by Treatment Arm

Treatment	Dose Level	Dose	Number of Subjects
VX-150	1 (highest)	First dose 1500 mg, then 750 mg q12h	44
	2	1000 mg qd	44
	3	500 mg q12h	44
	4	First dose 500 mg, then 250 mg q12h	44
	5 (lowest)	250 mg qd	22
Placebo			44

[figure not shown]
q12h: every 12 hours; qd: daily

Note: q12h dosing will be through 36 hours after the first dose of study drug throughout the protocol.

Randomization will be stratified by site and sex. To maintain the blind, all subjects will receive the same number of capsules in a double-dummy design.

Subjects will report their pain on the NPRS at scheduled time points (Table 3-2) through 48 hours after the first dose of study drug. In addition, pain intensity will be recorded on the NPRS immediately before each administration of rescue medication. Subjects are encouraged to wait 90 minutes after the first dose of study drug to receive rescue medication, and subjects should generally not receive rescue medication unless their NPRS is ≥4. However, subjects may receive rescue medication at any time after the first dose of study drug per their request. The rescue medication will be ibuprofen (400 mg [oral] every 4 hours [q4h] as needed [prn]).

Figure 9-1 VX18-150-104 Study Design

CRU: clinical research unit; NPRS: Numeric Pain Rating Scale; VRS: Verbal Categorical Rating Scale
Notes: After removal of the popliteal sciatic block, a subject can be randomized once the subject requests the first

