7 STUDY DESIGN

7.1 Overall Design

This is a Phase 2B randomized, double-blind, placebo-controlled, dose ranging, 6-arm, parallel-design study. Subjects will receive a primary unilateral first metatarsal bunionectomy repair on Day -1 (Figure 7-1). A continuous popliteal sciatic block infusion (0.2% ropivacaine) will be started after surgery and will be removed between 3AM and 5AM on Day 1. After removal of the popliteal sciatic block, a subject can be randomized once the subject requests the first dose of study drug for pain relief, and the subject's pain is ≥4 on the NPRS and is moderate or severe on the VRS (Verbal Categorical Rating Scale). If a subject does not meet the NPRS and VRS criteria within 9 hours of removal of the popliteal sciatic block, the subject will not be eligible to enroll in the study.

A total of approximately 242 subjects will be randomized 2:2:2:2:1:2 to 6 treatment arms, evaluating a range of 5 VX-150 dose levels as shown in Table 7-1.

Table 7-1 VX-150 Doses by Treatment Arm

Treatment	Dose Level	Dose	Number of Subjects
VX-150	1 (highest)	First dose 1500 mg, then 750 mg q12h	44
	2	1000 mg qd	44
	3	500 mg q12h	44
	4	First dose 500 mg, then 250 mg q12h	44
	5 (lowest)	250 mg qd	22
Placebo			44

[figure not shown]
q12h: every 12 hours; qd: daily

Note: q12h dosing will be through 36 hours after the first dose of study drug throughout the protocol.

Subjects will report their pain on the NPRS at scheduled time points (See Table 3-2 in CSP) through 48 hours after the first dose of study drug. In addition, pain intensity will be recorded

on the NPRS immediately before each administration of rescue medication. Subjects are encouraged to wait 90 minutes after the first dose of study drug to receive rescue medication, and subjects should generally not receive rescue medication unless their NPRS is ≥4. However, subjects may receive rescue medication at any time after the first dose of study drug per their request. The rescue medication will be ibuprofen (400 mg [oral] every 4 hours [q4h] as needed [prn]).

Figure 7-1 VX18-150-104 Study Design

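### The SAP's baseline fallback for an incomplete first-dose time cannot return a valid NPRS or VRS baseline: it gives a score from before block removal or none at all

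*SAP*

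**What the plan says.** The SAP describes the NPRS baseline in four places.

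- SAP 9.1: "Baseline value for NPRS will be defined as the most recent non-missing measurement collected on Day 1 before the first dose of study drug". This rule is specific to NPRS; other variables have a separate rule.
- SAP 9.3.1.1: each pain intensity difference is taken from the score given when the subject requests the first dose.
- SAP Appendix A, table: the baseline window for both NPRS and VRS is "After removal of the popliteal sciatic block, Pre-dose Day 1".
- SAP Appendix A, note 3: "When define efficacy and safety at baseline, refer to the generic baseline definition in Section 9.1". The note then adds that, if the hour and/or minute of first dose is missing, "baseline will be defined as the most recent non-missing measurement collected before the date of first dose of study drug". It states no exception for NPRS or VRS.

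On timing, SAP 7.1 says the block infusion "will be started after surgery and will be removed between 3AM and 5AM on Day 1", and Protocol 9.1 agrees. Inclusion criterion 6 (Protocol 8.1) requires the qualifying pain scores "within 9 hours after removal of the popliteal sciatic block on Day 1". A footnote to Protocol Table 3-2 says that "pain intensity on the NPRS will be recorded when the subject requests the first dose of study drug for pain relief"; the VRS is taken at the same moment.

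**The concern.** The first three statements place the baseline on Day 1, after block removal and before dosing. The fallback in note 3 works by date and so rules out everything recorded on the day of dosing. A programmer who follows note 3 literally and one who follows 9.1 would derive different baselines for the same subject.

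The NPRS baseline enters every term of SPID24, serves as a covariate in the primary ANCOVA (SAP 9.3.1.2), and appears in both numerator and denominator of the percentage reduction that defines a responder (SAP 9.3.2.1). A wrong value carries through all three, and a missing value leaves all three without an input. The VRS baseline is used only descriptively (SAP 9.2.2), so less depends on it.

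**Working it through.** The plan gives no figure to reproduce here. The check has four steps.

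**1. Can any valid baseline score predate the date of first dose?**
Inputs: block removal at 03:00 to 05:00 on Day 1 (Protocol 9.1, SAP 7.1); qualification within 9 hours (Protocol 8.1).
Latest qualifying time = removal time + 9 h: 03:00 + 9 h = 12:00, and 05:00 + 9 h = 14:00, both on Day 1.
Block removal, the qualifying scores and the first dose therefore share one calendar date. No score can meet both the Appendix A window and the fallback.

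**2. What can the fallback select?**
Protocol Table 3-2 schedules NPRS and VRS from Day 1 only. Protocol 9.4.1 uses NPRS thresholds after surgery, with the block in place, to guide supplemental analgesia, so NPRS scores dated Day -1 may exist. The documents do not say that they are entered in the database. No use of the VRS before Day 1 is described. For NPRS the result is a score from before block removal or nothing; for VRS it is most likely nothing.

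**3. Effect on SPID24 if a score is selected**
SPID24 = Σ wᵢ × (B − xᵢ), where B is the baseline, xᵢ the score at time i and wᵢ the hours since the previous assessment.
Weights from the Table 3-2 times (0.5, 1, 1.5, 2, 3, 4, 5, 6, 8, 12, 16, 20, 24 h): 4 × 0.5 + 4 × 1 + 1 × 2 + 4 × 4 = 2 + 4 + 2 + 16 = 24.
Error = 24 × (fallback baseline − request score).
The SPID24 formula as printed in SAP 9.3.1.1 leaves out the 6-hour term, so its weights sum to 23.

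All scores below are assumptions; the documents give none.

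| Request score | Fallback score | Error, weights 24 | Error, weights 23 |
|---|---|---|---|
| 7 | 1 | 24 × (1 − 7) = -144 | 23 × (1 − 7) = -138 |
| 7 | 3 | 24 × (3 − 7) = -96 | 23 × (3 − 7) = -92 |
| 4 | 0 | 24 × (0 − 4) = -96 | 23 × (0 − 4) = -92 |
| 10 | 0 | 24 × (0 − 10) = -240 | 23 × (0 − 10) = -230 |
| 4 | 7 | 24 × (7 − 4) = +72 | 23 × (7 − 4) = +69 |

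The last row is possible because Protocol 9.4.1 itself foresees scores of 4 to 6, and of 7 or above, while the block is in place.

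**4. Effect on responder status**
Reduction = 100 × (B − x₂₄) / B, with assumed scores again:

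| Request / fallback / 24 h | With request score | With fallback score | Status |
|---|---|---|---|
| 7 / 2 / 3 | 100 × 4/7 = 57.1% | 100 × (−1)/2 = -50% | loses the 30% and 50% levels |
| 5 / 8 / 3 | 100 × 2/5 = 40% | 100 × 5/8 = 62.5% | gains the 50% level |
| 7 / 5 / 1 | 100 × 6/7 = 85.7% | 100 × 4/5 = 80% | unchanged |

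A fallback score of 0 makes the percentage undefined. That cannot happen with a qualifying score, which must be at least 4.

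**The case against.** Four points can be made for the plan.

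- **The specific rules should prevail.** SAP 9.1 has a rule for NPRS alone, 9.3.1.1 ties the pain difference to the request for first dose, and the table window agrees. Note 3 refers to a generic definition, so it can be read as yielding to these. That reading is sensible, but the SAP does not state it, and note 3 names efficacy explicitly.
- **The trigger is rare.** Doses are given under direct supervision (Protocol 10.6). Dose date and time go into the source document on PK sampling days (Protocol 11.2.1), intake time is collected (Protocol 12.3.2.4), two stopwatches start at the first dose (Protocol 11.4), and missing data are queried (Protocol 13.3). This stands and sets the size of the point. It does not make the rule correct, and the SAP itself chose to provide for the case.
- **A missing dose time harms more than baseline.** The post-dose NPRS windows of ±5 or ±10 minutes also need that time. This is true, and a corrected baseline would not repair them. It is no reason to discard a baseline that is known without the clock.
- **For ECG and vital signs the fallback is defensible.** The Appendix A windows for both start at the screening visit, so an earlier record is permitted. This stands, and the point is confined to NPRS and VRS.

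Two stronger readings are tempting. A reader might infer that the fallback always picks a low score under block and so biases SPID24 downward. The documents do not support this: no section shows that Day -1 scores reach the database, Appendix A note 1 treats a visit with nothing in its window as missing, and a score under block may exceed the request score. A reader might also divide the illustrative shift by 44 subjects (-96/44 = -2.2; -144/44 = -3.3) and call it the bias in an arm. That is a raw mean on assumed scores. The analysis adjusts for the same baseline, so the effect on the adjusted comparison differs and cannot be derived from what the plan gives.

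**Conclusion.** For NPRS and VRS, the fallback in note 3 contradicts SAP 9.1, SAP 9.3.1.1 and the windows in its own table. Followed as written, it can return a score from before block removal or no baseline, never the intended one. This conclusion rests only on the stated removal times, the 9-hour limit and the wording of note 3.

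For an affected subject, SPID24 moves by 24 points per NPRS point of baseline error (23 with the formula as printed), with unknown sign, and responder status may or may not change. If no earlier score is on file, SPID24, the covariate and the percentage reduction cannot be computed from the baseline that note 3 prescribes. The particular scores used above are assumptions.

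The practical impact on the trial is small, since few or no subjects should lack a complete first-dose time. This is a consistency correction; the documents give no ground for doubting the primary analysis as a whole.

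**What to change.** Add one sentence to note 3 of SAP Appendix A: the date-based fallback does not apply to NPRS or VRS, whose baseline is the Day 1 score recorded when the subject requested the first dose, whether or not the clock time of dosing is complete. That score is pre-dose by its nature, so no clock time is needed to identify it.

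Optionally, the same sentence can allow a Day 1 ECG or vital-sign record labelled as pre-dose to be kept as baseline.

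The cost is one sentence in the SAP before database lock and a matching line in the derivation program. No additional data are needed.
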